
et al., 2013) will assess the level to which one perceives that others are having rewarding experiences while one is absent.

Personal goals will be appraised (during Baseline only) by having students write the top 5 goals they hope to achieve and will also be asked the extent to which they think using alcohol at differing levels will affect their goals. Other substance use, including co-use cognitions and behaviors, will be assessed for lifetime and past month frequency using the Customary Drinking and Drug Use Record ($\alpha = .70\text{-.94}$; Brown et al., 1998; Schafer & Brown, 1991) as well as an adapted version that assesses co-use of substances. Drinking motives (only at 6-week and 3-month) will be assessed using the Drinking Motives Questionnaire (Grant et al., 2007). Marijuana-use will be assessed using items about their lifetime, past-year, and past-month marijuana-use frequency using the Marijuana Monitoring the Future Questionnaire. Reasons for Limiting Marijuana Use will be assessed using a modified version of the Reasons for Not Drinking Scale ($\alpha = .79$; Huang, 2011) and the Motives for Abstaining from Alcohol Questionnaire- Modified (Stritzke & Butt, 2001). To determine prescription stimulant misuse, items will be added at 6-week and 3-month only over this topic. Academic Motivation (only at 6-week and 3-month) will be assessed using the Academic Motivation Scale ($\alpha = .81$; Vallerand et al., 1992). Peer Pressure will be assessed using the Peer Pressure Scale (Santor et al., 2000). Protective Behaviors will be measured at 6-week and 3-month only using the Protective Behavioral Strategies Scale - 20 (Treloar et al., 2015). Thoughts on alcohol use during college will be assessed at 6-week and 3-month only using the College Life Alcohol Salience Scale (Osberk et al., 2010). Loneliness (only at 6-week and 3-month) will be assessed using the Three Item Loneliness Scale ($\alpha = .72$; Hughes et al., 2004). Anxiety and depression will be measured at 6-week and 3-month only using the PROMIS Anxiety scale v1.0 ($\alpha = .96$; Cella et al., 2010) and the PROMIS Depression scale ($\alpha = .96$; Cella et al., 2010). Social psychological aspects of COVID-19 will be measured (only at 6-week and 3-month) using the Conway COVID-19 Measure (Conway et al., 2020).

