For participants assigned to TM intervention condition, acceptability will be assessed with responses from a brief satisfaction survey included in the 6-week post-intervention assessment. Acceptability will be determined by (1) the proportion of participants who find the intervention acceptable (e.g., acceptability of content delivery method), usable (e.g., ease of viewing and interacting with TM intervention content), relevant (e.g., relevance of material), and helpful (e.g., finding content helpful, beneficial, important), (2) whether participants shared the texts with anyone else, (3) the proportion of participants who would recommend the study, and (4) the proportion of participants who found the program to be favorable overall.

Intervention Materials.

After baseline survey completion, participants assigned to TM intervention will receive 6 weeks of TMs.

Intervention Condition. The content for the TM Intervention will be designed to be non-confrontational in tone, seek to increase motivation to drink lightly or not at all, and based both on general information about light and non-drinking as well as information provided during the baseline assessment. Text messages will fall into 5 basic categories (images, norms, goals, protective behavioral strategies tips, and alternative activities) and will be randomly provided to participants from a master list of text messages. Please see Appendix C for a list of Text Messages. All TMs will be under 160 characters so that they may be read by all phone models and plans. The TM intervention condition will be programmed using Rivulent Inc. and will be linked with the data entry module for the baseline assessment, thereby allowing data to be imported directly from the survey into the feedback. Rivulent will randomly assign eligible participants to either the TM condition or the control (Assessment Only) condition. Participants will know they have been assigned to this condition when they receive the 6-week Intervention Reminder Email (1) informing them of their intervention start and end dates. They will also receive a 6-week intervention reminder text message. If they are in the TM group and choose to no longer participate in the study, participants can contact the Freshman Experience Project Staff and ask to be removed.

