To explore treatment differences and to determine preliminary effect sizes in drinking outcomes, this pilot will have five repeated measures (i.e., baseline, 6-week post-intervention, 3, 6, and 9-month follow-ups), yielding up to 1500 Level 1 observations (repeated-measures) across 300 Level 2 cases (people). Prior to inferential statistics, univariate and bivariate descriptive statistics will be used to assess distributions and simple associations among variables. Primary outcomes are alcohol initiation (binary outcome) and escalation in terms of number of drinks and consequences (both count outcomes). Additional outcomes are abstainer prototype favorability, abstainer injunctive and descriptive norms, engagement in and enjoyment of alternative activities, and endorsement of personal goals that do not involve alcohol, which are modeled as normally distributed outcomes. Given the repeated measures design, generalized linear mixed models (GLMM; Raudenbush & Bryk, 2002) will be used. GLMM (aka hierarchical generalized linear models) allow for non-normal outcomes and missing data. The model below represents the basic analytic model for a count outcome:

$$\text{Level 1: } \log(E[DV_{ti}]) = \pi_{0i} + \pi_{1i}(6\text{-week})_{ti} + \pi_{2i}(3\text{-month})_{ti} + \pi_{3i}(6\text{-month})_{ti} + \pi_{4i}(9\text{-month})_{ti} \quad (1)$$

$$\begin{aligned} \text{Level 2: } \pi_{0i} &= \beta_{00} + \beta_{01}(Tx)_i + r_{00i} & \pi_{3i} &= \beta_{30} + \beta_{31}(Tx)_i + r_{30i} \\ \pi_{1i} &= \beta_{10} + \beta_{11}(Tx)_i + r_{10i} & \pi_{4i} &= \beta_{40} + \beta_{41}(Tx)_i + r_{40i} \\ \pi_{2i} &= \beta_{20} + \beta_{21}(Tx)_i + r_{20i} \end{aligned}$$

where t indexes time point and i indexes participants. DV_{ti} represents the outcome for each individual at each time point. Time will be coded with *four* dummy variables (6-week $_{ti}$, 3-month $_{ti}$, 6-month $_{ti}$, and 9-month $_{ti}$) that compare follow-up assessments to baseline (reference category). Tx is a dummy coded variable comparing the TM intervention condition to the AOC condition. We will test sex and age in all analyses. We will determine preliminary effect sizes using the

model shown in equation 1. The four treatment by time interactions (β_{11} to β_{41}) compare the change in the outcome since baseline between intervention and control.

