Online screening survey: 5-10 minutes

Online baseline survey: 45 minutes

6 weeks Intervention Content: 1-2 minutes per text message

Online 6-week, 3-month surveys: 45 minutes

Online 6-month, 9-month surveys: 25-30 minutes

Online interview: 60 minutes

F. Human Subjects - Describe the characteristics of the research population:

- 1) *Sample Size*: Number of subjects to be enrolled in this study at this site. Approximately 300 subjects at 1 sites in the U.S. will be enrolled in the study overall. Half of the subjects (150) will be randomized to the TM intervention and the other half to the control group.
For Clinical Trial studies, indicate number of subjects to be randomized N/A
- 2) Describe both *Inclusion AND Exclusion Criteria*. BE SPECIFIC! Also, if children (persons under age 18) are excluded from this study provide scientific justification for such exclusion. Include physical, mental, cognitive, medical, and other relevant Inclusion and Exclusion criteria.

Inclusion criteria:

- 1) Age 18-19 (If a participant screens in at age 19 and turns 20 prior to the start of the pilot study, the participant will be allowed to be in the research study.)
- 2) Birthdate that is consistent with their given age

- 3) First-year college student at the University of North Texas
- 4) Valid email address
- 5) Provide a valid mobile phone number and have a text messaging plan on their mobile phone
- 6) Consumed alcohol on average once a week or less in the last month
- 7) No episodes in the past month of consuming 5/4 drinks in the past month for men/women
- 8) Used marijuana once a week or less on average in the last month
- 9) Express any level of willingness to take a sip of alcohol
- 10) If female, must not be pregnant or trying to get pregnant
- 11) Have not received treatment for alcohol use
- 12) Willing to participate in the pilot study

Exclusion criteria include not meeting inclusion criteria, unwillingness to participate, failure to provide consent (e.g., declining participation in the study), providing inconsistent responses (e.g., age) identified by the survey, and having already participated in the study (IRB 2018-128 or this protocol) as identified by overlap or consistency in computer IP addresses, contact information, and demographics.

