**REFINING AND PILOTING A TEXT MESSAGING INTERVENTION TO DELAY
ALCOHOL INITIATION AND REDUCE ALCOHOL USE ESCALATION AMONG
ABSTAINER AND LIGHTER DRINKER COLLEGE STUDENTS**

**NCT03750838
11/16/2023**

Analytic Plan

To assess feasibility of the intervention, we examined targeted recruitment, enrollment, and retention rates. To feasibility, we examined response rates for text message intervention rating for those assigned to the intervention condition. For acceptability, we assessed overall ratings of acceptability as well as mean ratings of content area-specific text messages. Rates of alcohol initiation (yes/no) were examined at each time point as were means and standard deviations of the number of drinks per week at each time point.

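### Protocol equation 1 takes effect sizes from change since baseline with a free baseline arm difference: unbiased under randomisation, but generally less precise than using the baseline already collected

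*Protocol*

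**What the plan says.** **Model (Protocol, Data Analysis and Power).** Equation 1 treats baseline as the first of five outcome rows and as the reference category for time. The person-level intercept is β00 + β01(Tx) + r00, so the arms may differ at baseline by an estimated amount. The protocol says "We will determine preliminary effect sizes using the" model in equation 1, and describes β11 to β41 as the terms that "compare the change in the outcome since baseline between intervention and control". Sex and age are the only covariates named. Nothing sets β01 to zero, and the baseline value of the outcome is not a covariate.

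**Design (Protocol, Intervention Materials).** "Rivulent will randomly assign eligible participants to either the TM condition or the control (Assessment Only) condition". "After baseline survey completion, participants assigned to TM intervention will receive 6 weeks of TMs". On knowledge of arm: "Participants will know they have been assigned to this condition when they receive the 6-week Intervention Reminder Email". That email is not dated relative to the baseline survey.

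**Measures (Protocol, baseline and follow-up measures).** Behaviour is asked about over the lifetime at baseline, and over 6 weeks or 3 months afterwards. "Personal goals will be appraised (during Baseline only"), although endorsement of goals is listed among the normally distributed outcomes.

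**SAP, Analytic Plan.** The SAP is dated after the protocol. For drinks it gives "means and standard deviations of the number of drinks per week at each time point" and contains no mixed model.

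**The concern.** In a randomised comparison the baseline arm difference has expectation zero, provided baseline is measured before assignment can influence it. Letting the model estimate that difference and then subtracting it carries the chance imbalance at baseline in full into every follow-up contrast. Setting it to zero, or using baseline as a covariate, removes only the part that baseline predicts.

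The stake is the width of the intervals. Aim 3 wants preliminary effect sizes for planning a future R01, and equation 1 is their only stated source. The point applies to the counts (drinks, consequences) and to normal outcomes measured at both baseline and follow-up. Two outcomes fall outside. Among baseline abstainers the baseline value of initiation is constant, so there is no baseline noise to remove. Personal goals have no follow-up measurement and hence no contrast.

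**Working it through.** **The plan's own figure.** 300 people × 5 occasions = 1500 observations, as stated. Half of 300 gives 150 per arm (Protocol, Human Subjects). The documents give no alpha, power, SD, correlation or dropout for the effect sizes, so ρ and k below are assumed.

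**Normal outcomes.** With n per arm, complete data and follow-up SD of 1:

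- Change contrast (β01 free): variance = (2/n)(1 + k² − 2ρk).
- Baseline-constrained or baseline-adjusted contrast: variance = (2/n)(1 − ρ²).
- Ratio = (1 + k² − 2ρk)/(1 − ρ²) = 1 + (k − ρ)²/(1 − ρ²). It is never below 1 and equals 1 when k = ρ.

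Example, k = 1, ρ = 0.5: 1 + 0.25/0.75 = 1.33.

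| k | ρ = 0.3 | ρ = 0.5 | ρ = 0.7 |
|---|---|---|---|
| 0.5 | 1.04 | 1.00 | 1.08 |
| 1 | 1.54 | 1.33 | 1.18 |
| 1.5 | 2.58 | 2.33 | 2.25 |

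A five-occasion generalised least squares calculation, with correlations among follow-ups of 0.6 and 0.75, gives the same nine ratios.

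At k = 1 and n = 150 per arm:

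| ρ | SE, change | SE, baseline used | 95% half-widths | Per arm for change contrast to match 150 |
|---|---|---|---|---|
| 0.3 | 0.137 | 0.110 | 0.268 vs 0.216 | 150 × 1.538 = 230.8, so 231 |
| 0.5 | 0.115 | 0.100 | 0.226 vs 0.196 | 150 × 1.333 = 200 |
| 0.7 | 0.089 | 0.083 | 0.175 vs 0.162 | 150 × 1.1765 = 176.5, so 177 |

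**Count outcomes.** Equation 1 was reduced to baseline plus one follow-up, with Poisson counts and two correlated lognormal random effects (correlation 0.6), 150 per arm. It was fitted by maximum likelihood with and without β01. All inputs are assumed. The last column puts the marginal coefficients of variation and marginal correlation into the closed form above.

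| Means, baseline/follow-up | Random-effect SDs | SE of log rate ratio, free vs constrained | Likelihood variance ratio | Closed form |
|---|---|---|---|---|
| 0.8/2.0 | 0.8/1.0 | 0.193 vs 0.148 | 1.70 | 1.53 |
| 0.8/2.0 | 1.0/1.0 | 0.203 vs 0.146 | 1.92 | 1.78 |
| 0.4/1.5 | 1.0/1.0 | 0.247 vs 0.158 | 2.47 | 2.23 |
| 1.0/2.0 | 0.6/1.2 | 0.196 vs 0.173 | 1.28 | 1.16 |

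In the first row the 95% limits lie at the estimate ×/÷ exp(1.96 × 0.193) = 1.46, against exp(1.96 × 0.148) = 1.34.

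Simulation of 600 trials gave ratios of 1.65, 1.91 and 1.30 for rows 1, 2 and 4, with mean estimates within 0.02 of the true value of 0. A separate simulation with other inputs and only 120 replicates per setting gave 1.43 to 1.62, with both models centred near the true log rate ratio of −0.25.

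The closed form falls short of the likelihood result in every row, so for counts it is a rough guide only. The five-occasion count model was not fitted, and baseline as a covariate was not computed for counts.

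**The case against.** **This is a valid, conventional analysis in a pilot with no precision target.** That stands, and it is why the point is minor. A reader might infer that the effect sizes are biased or the model wrong. The documents do not support that: with random assignment and an uncontaminated baseline, both contrasts estimate the same quantity.

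**The SAP does not use the model.** This also stands. A reader might infer that reported results are affected, but the SAP's summaries do not involve equation 1. The point survives for the protocol because the SAP names no other source of effect sizes.

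**R01 planning also draws on base rates and variances.** True, and the change would not materially improve those. It helps only the effect sizes.

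**The exact figures are for normal outcomes, while the primary outcomes are initiation and counts.** Correct. The count figures rest on a two-occasion substitute and assumed inputs. The lifetime recall window at baseline means that even comparable baseline and follow-up means cannot be presumed.

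**Entry limits.** One criterion reads "Consumed alcohol on average once a week or less in the last month". It is tempting to say that such limits shrink the loss by reducing baseline variation. They should also lower the baseline mean, which adds relative Poisson noise, and the lowest-mean setting gave the largest ratio (2.47). The direction is not established.

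**The constraint depends on timing.** Assignment is of eligible participants, and eligibility is set at screening, before the baseline survey. If arm were known by then, equality at baseline would no longer follow from randomisation. This stands as a condition on the fix.

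**Conclusion.** The point holds as a matter of precision, not validity, and is worth considering rather than essential. For normal outcomes measured at baseline and follow-up, equation 1's contrast has 1 + (k − ρ)²/(1 − ρ²) times the variance of one that uses baseline: 1.54, 1.33 and 1.18 at ρ 0.3, 0.5 and 0.7 if k = 1, and no loss if k = ρ. For counts the illustrative range is 1.28 to 2.47. No single figure should be quoted as this trial's loss.

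The conclusion rests on random assignment, baseline answered before participants learn their arm, complete data, large samples, and assumed values of ρ, k and the count inputs. It does not extend to initiation among baseline abstainers, to personal goals, or to the SAP's descriptive analysis.

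**What to change.** For the count outcomes, and the normal outcomes with follow-up data, do one of the following:

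- remove β01(Tx) from the intercept line of equation 1; or
- model the four follow-ups with the baseline value as a covariate, on a stated scale for counts, such as log(baseline + 1).

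The second sits more naturally with the differing recall windows, since a lifetime report is better adjusted for than subtracted. Report the arm contrast at each follow-up as the effect size, and name the outcomes covered.

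State that the baseline survey is completed before participants learn their arm. If that cannot be confirmed, keep β01 free, so that the model does not impose an equality the design no longer guarantees.

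The cost is one term removed, or one covariate with its scale specified, plus two or three sentences. No new data are needed. In the large-sample calculations for normal outcomes, using baseline never loses precision.

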The first question that participants will be asked in the screening survey is their age. Thereafter, the remaining survey items will be based on show-if survey logic, so that participants who mark their age as 18-19 will continue receiving screening survey questions. Participants who provide consent and are age 18-19 will receive demographic questions (i.e., birth sex, race, ethnicity,

pregnancy status) and items that assess their current levels of drinking as well as crucial eligibility questions such as "Are you a first year college student at the University of North Texas" and "Are you willing to participate in 6-week text-messaging intervention during the start of the fall semester?" All participants will be asked for basic demographics (including age, birth sex, birth date, race/ethnicity, pregnancy status if female, etc.) and for contact information during the online screening.

Individuals who indicate they are 17 or younger, or 20 and over will be automatically rerouted to the end of the survey using show-if logic, and those who indicate they have participated in alcohol treatment will be deemed ineligible. These ineligible participants will not receive any additional questions. Data from anyone age 17 or younger, or 20 and over will not be kept. If participants are deemed ineligible on any of the inclusion/exclusion criteria, they will be routed to an ineligible end page that will thank them for their time and inform them that they are not a fit for the present study. They will also receive an email informing them that they are not eligible for the study. The data of participants who are ineligible will not be saved or used in anyway. Data for ineligible participants will be dropped every 30 days and will not be used in any analyses.

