Screening Survey Consent. We are requesting informed consent for the screening survey to be obtained online with an electronic signature because the first part of the study (i.e., screening) is administered online. After receiving information about the study and being presented with the online screening informed consent statement, individuals will be asked to complete an electronic signature before being directed to participate in the online screening survey, which will determine whether or not they are a good fit for the study. If a participant wishes to not provide consent for the survey (i.e., they select “No, I choose not to participate” on the consent form), they will immediately be routed to the screening decline page and will not be shown any additional information or be asked to enter any additional information. Thus, a non-consenting participant cannot proceed further. The electronic signature will be requested via a

text box where participants can draw their signature. This electronic signature would include a date and time stamp. Participants will also be asked to type their full legal name and a valid email. Survey programming will not move participants who do not provide consent to the HIPAA form. Participants who do not provide consent would be moved to the end page. Survey programming will be done such that participants cannot advance to the Screening Survey until both consent to participate and HIPAA Authorization has been provided. If a participant does not consent or provide a valid email, they will be routed to the end page and will not be shown the HIPAA Authorization or any survey items. Participants who are eligible will receive an email informing them of their eligibility as well as a link to the Baseline Informed Consent and HIPAA authorization form. Participants who are ineligible will receive an email notifying them of their ineligibility and thanking them for their time. All participants who provide an email will receive a link to a copy of their signed consent form and HIPAA forms if relevant.

If we do not receive the completed screening consent and HIPAA form, we will periodically send reminders – via email (up to 5).

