Baseline Consent. We are requesting informed consent for the full study to be obtained online prior to the baseline assessment with an electronic signature because all assessments (i.e., baseline, 6-week, 3, 6, and 9-month follow ups) are administered online. After receiving information about the study and being presented with the online baseline informed consent statement, individuals will be asked to complete an electronic signature before being directed to participate in the online baseline survey. If a participant wishes to not provide consent for the survey (i.e., they select “No, I choose not to participate” on the consent form), they will immediately be routed to the baseline decline page and will not be shown any additional information or be asked to enter any additional information. Thus, a non-consenting participant cannot proceed further. The electronic signature will be requested via a text box where participants can draw their signature. This electronic signature would include a date and time stamp. Participants will also be asked to type their full legal name. Survey programming will not move participants who do not provide consent to the HIPAA form. Participants who do not provide consent would be moved to the end page. Survey programming will be done such that participants cannot advance to the subsequent survey items until both consent to participate and HIPAA Authorization has been provided. If a participant does not consent, they will be routed to the end page and will not be shown the HIPAA Authorization or any survey items. All participants who provide an email will receive a link to the copy of their signed consent form and HIPAA forms if relevant.

If we do not receive the completed baseline consent and HIPAA form, we will periodically send reminders – via email (up to 5), text (up to 5) and/or phone/voicemail (up to 3).

Post-Intervention Interview Consent Document. We are requesting informed consent for the post-intervention interviews to be obtained online prior to the interview with an electronic signature because all interview procedures will take place online. After receiving information about the post-intervention interviews and being presented with the online post-intervention

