Participants who meet inclusion criteria will be emailed a study link. The link will take participants to an Informed Consent Statement and HIPAA authorization form, where they will be asked to indicate study consent through two electronic signatures: 1) study consent form, and 2) HIPAA authorization form. The electronic signatures will be requested via a text box where participants can draw their signature. If participants indicate consent to the study, they will continue to the baseline survey. The baseline survey will include questions about demographics, personality, drinking and drug use, and other health behaviors and will take approximately 45 minutes to complete. Questions in the assessments will also include topics about sexual orientation, sexual experience, sexual desire, religion, and relationship status. Participants will receive an email and text message reminder that their follow-up surveys is approaching 5 days before their scheduled invitation date. We will also mail participants a letter with an incentive item valued at no more than \$10 and call them shortly before the survey invitations are sent. If we do not receive the completed assessment at each follow-up (Baseline Assessment, 6-week, 3, 6, and 9-Month assessment), we will periodically send reminders – via email (up to 8), text (up to 8) and/or phone/voicemail (up to 3). Participants can earn \$20 for baseline, \$25 for the 6-week follow-up, \$30 for the 3-month follow-up, \$35 for the 6-month follow-up, \$40 for the 9-month follow-up.

Post-Intervention Interview.

A total of 15 randomly selected participants assigned to the intervention condition and who agreed to be contacted for future research opportunities will be compensated \$50 for the post-intervention interview.

Recruitment Stratification.

We will stratify recruitment based on age, biological sex, and ethnicity, aiming to match demographics of UNT.

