After all interviews have been conducted, we will notify remaining invited participants that their participation is no longer needed.

Data Analysis and Power.

Data Analysis. In order to evaluate the pilot study, we will examine (a) recruitment and retention rates and (b) satisfaction surveys (i.e., accessible, usable, convenient, relevant, and helpful) and (c) rates of alcohol initiation and escalation, negative consequences, abstainer prototype favorability, abstainer injunctive and descriptive norms, engagement in and enjoyment of alternative activities, and endorsement of personal goals that do not involve alcohol, which will provide base rates and variance in outcomes to determine adequate power for a future clinical trial R01 application.

Feasibility will be assessed by (1) the proportion of first-year college students ages 18-19 who meet inclusion criteria and enroll for the study and (2) the proportion of participants who complete the TM intervention, the 6-week post-intervention assessment and 3, 6, and 9-month follow-ups compared to assessment only control. The length of time to recruit our target enrollment will be assessed as an outcome of feasibility.

Acceptability will be assessed with responses from a brief satisfaction survey included in the 6-week post-intervention assessment. Acceptability will be determined by (1) the proportion of participants who find the intervention acceptable (e.g., acceptability of content delivery method), usable (e.g., ease of viewing and interacting with TM intervention content), relevant (e.g., relevance of material), and helpful (e.g., finding content helpful, beneficial, important), (2) participants' ratings of individual TMs, (3) whether participants shared the texts with anyone else, (4) the proportion of participants who would recommend the study, and (5) the proportion of participants who found the program to be favorable overall. Responses from the post-intervention interviews will also be used as a measure of acceptability.

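### Students who fit the target population but decline the texts at screening are classed as ineligible and dropped, so an enrolment rate among eligible students overstates uptake

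*Protocol*

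**What the plan says.** **Eligibility.** Protocol section F, item 2 has twelve inclusion criteria, the last being "Willing to participate in the pilot study". The sentence after them reads "Exclusion criteria include not meeting inclusion criteria, unwillingness to participate, failure to provide consent (e.g., declining participation in the study" and goes on to inconsistent responses and earlier participation. Consent appears only in that sentence, not among the twelve.

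**Screening.** The screening-survey text under General Recruitment gives, as an example of a crucial eligibility question, "Are you willing to participate in 6-week text-messaging intervention during the start of the fall semester". A student who fails any criterion is sent to an ineligible end page. Ineligible students' data are deleted every 30 days and kept out of all analyses; the Data Storage section repeats the deletion.

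**Order of steps.** Under Screening Survey Consent: "Participants who are eligible will receive an email informing them of their eligibility as well as a link to the Baseline Informed Consent". Under the baseline and follow-up assessments: "Participants who meet inclusion criteria will be emailed a study link". Under Baseline Consent, a student who declines goes to a baseline decline page, and for the rest: "If we do not receive the completed baseline consent and HIPAA form, we will periodically send reminders".

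**Feasibility measure.** Data Analysis and Power gives as the first measure "the proportion of first-year college students ages 18-19 who meet inclusion criteria and enroll for the study". The SAP's Analytic Plan says "To assess feasibility of the intervention, we examined targeted recruitment, enrollment, and retention rates". Neither names a denominator or a target rate.

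**The concern.** In an efficacy trial, listing willingness as an entry criterion is harmless, because uptake is not an outcome. Here enrolment is a named feasibility outcome, feasibility is part of Aim 3, and the pilot is meant to inform a larger R01 application. The Background itself argues from how readily abstainers and lighter drinkers join text-message studies.

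A student who meets criteria 1-11 and does not want six weeks of texts is exactly the refusal a feasibility study should count. Under the stated rules that student is recorded as ineligible and then deleted. Apparent ineligibility goes up, apparent refusal goes down, and a recruitment plan that treats the resulting rate as uptake in the target population would understate how many such students must be approached.

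**Working it through.** The documents state no enrolment proportion, so there is no figure to reproduce. The check is which students each possible denominator contains.

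**Notation**
- N = students who complete the screener, meet criteria 1-11 and are not excluded for inconsistent responses or prior participation
- w = share of N who say they are willing at screening
- c = share of those who give baseline consent
- b = share of consenters who complete enrolment
- Enrolled = N × w × c × b

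**Inputs.** Enrolled = 300 is the protocol's target (section F, item 1). The values of w, c and b are not in the documents. I assume w = 0.80, c = 0.70, b = 0.98 for illustration, with ranges w 0.60-0.95, c 0.50-0.90, b 0.90-1.00.

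**Working back from 300.** Consented = 300/0.98 ≈ 306. Passed the 12-item screen = 306.1/0.70 ≈ 437. Met criteria 1-11 = 437.3/0.80 ≈ 547.

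| Denominator | Rate | Illustration | Over the assumed ranges |
|---|---|---|---|
| Criteria 1-11 (target population) | w × c × b | 0.80 × 0.70 × 0.98 = 54.9% | 27.0% to 85.5% |
| All 12 criteria, before baseline consent | c × b | 0.70 × 0.98 = 68.6% | 45% to 90% |
| Literal exclusion list, non-consenters also removed | b | 98.0% | 90% to 100% |

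**Overstatement.** Dividing the second row by the first gives (c × b)/(w × c × b) = 1/w, which does not depend on c or b:
- w = 0.95: 1/0.95 = 1.05
- w = 0.80: 1/0.80 = 1.25 (68.6/54.9)
- w = 0.60: 1/0.60 = 1.67

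Dividing the third row by the first gives 1/(w × c). In the illustration that is 1/(0.80 × 0.70) = 1.79. Over the ranges it runs from 1/(0.95 × 0.90) = 1.17 to 1/(0.60 × 0.50) = 3.33.

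The direction needs no assumption: since w is at most 1, removing unwilling students from the denominator cannot lower the rate.

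**The baseline decliner.** Take a student who passes the 12-item screen and declines baseline consent. The exclusion sentence in section F makes that student excluded. The screening and baseline sections have already told the student that he or she is eligible, and use a separate decline page. The same person is in the denominator under one passage and out of it under the other.

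**All first-year students as the denominator.** The measure can also be read this way, and refusals then lower the rate. As a rough reference, 300 enrolled from a full set of 5,000 directory invitations is 300/5,000 = 6.0%. The other recruitment channels mean that this is not a closed pool. Such a rate also mixes refusal with genuine ineligibility, and the deletion rule removes the records needed to separate them.

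**The case against.** The strongest reply is that the protocol's own flow keeps most refusals visible. Eligibility is declared after screening and before baseline consent, decliners have their own page, and non-responders are reminded. The feasibility measure refers to inclusion criteria, and consent is not one of them. This stands. A reader might infer from the exclusion sentence that every refusal becomes an ineligible student and that the rate among eligible students is near 100% by construction. The documents do not support that: it holds only if the one sentence overrides the screening, consent and assessment sections.

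Second, the measure can be read with all 18-19-year-old first-year students as the denominator, so refusals would count. That is a fair reading, but neither document commits to it.

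Third, willingness is a separate screener item, so with every record kept one could count those who answered no. That is broadly right, provided the other criteria were also asked; the item order is not given. But the records are not kept. The documents mention no retained tallies, and the contact list kept for future research is not linked to survey answers.

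Fourth, time to reach target enrolment is measured separately, and naming willingness and consent as entry conditions is ordinary drafting. Both are true. Neither yields an uptake rate, and the fix below leaves the conditions for entering the trial unchanged.

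**Conclusion.** The point holds for refusals at the screening question. Followed as written, criterion 12 and the willingness item class students who meet criteria 1-11 but do not want the texts as ineligible, and the deletion rule drops their data. Any enrolment proportion based on eligible students then overstates uptake in the target population by 1/w. That is 1.05 to 1.67 for assumed w between 0.95 and 0.60; the true w cannot be obtained from the documents.

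For refusals at baseline consent the protocol contradicts itself. On its operational flow they stay in the denominator; on the literal exclusion list they leave it. A rate close to 100% belongs to that second reading alone and should not be presented as what the plan produces.

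The conclusion assumes that the denominator is eligible students, which the documents leave open, and that the screener question is how criterion 12 is applied. The trial's treatment comparison is not affected; the feasibility figure meant to inform the R01 is.

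**What to change.** 1. For the feasibility rate only, define eligible as meeting criteria 1-11 and not excluded for inconsistent responses or prior participation. Treat willingness and consent as enrolment steps.
2. Reconcile the exclusion sentence in section F with the screening and baseline consent sections, so that a baseline decliner has one status throughout.
3. State in the SAP that the rate is enrolled/eligible on this definition. Give separate counts for unwilling at screening, declined baseline consent, no response, and consented but baseline not completed.
4. Show students who decline screening consent in their own row. They never see the survey items, so their eligibility is unknown.
5. Keep de-identified counts of these categories before each 30-day deletion.

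The protocol places orientation recruitment in summer 2021 and the SAP is in the past tense, so the deletions may already have happened. If the counts are gone, say so and label the reported rate as conditional on stated willingness at screening.

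The cost is a few lines of protocol and SAP wording, a status code and a flow table. Randomisation, sample size and the intervention do not change. The reported enrolment rate becomes less favourable.
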